5.1.3 MASKING

Participants and Investigators will be masked to which lens type (brand) the participants will be wearing in each eye during the study in order to reduce bias towards or against any of the products. Lens packages/ blister will be overlabeled.

5.2 STUDY POPULATION

5.2.1 SAMPLE SIZE CALCULATION

The sample size required for a 2-tailed matched paired t-test to detect a change of 5 points in subjective ratings of handling for insertion and removal, with α =0.05, power = 0.90, and an effect size of 0.60 is 32 to complete the study and be eligible for data analysis (a sample size of 32 participants excluding possible dropouts and screen failures).

Up to 60 participants may be randomized to and dispensed with 1-Day ACUVUE Moist and Precision1 DD CLs, to account for potential drop-out in neophytes e.g. due to adaptation/handling issues.

5.2.2 NUMBER OF PARTICIPANTS

Up to 60 participants may be recruited using CORE records and advertising approved by the UW Office of Research Ethics. Up to 60 participants may be randomized to and dispensed with study products, with a target of number of 32 participants completing the study. Informed consent will be obtained for all participants prior to their enrolment in the study (Appendix 1).

5.2.3 INCLUSION AND EXCLUSION CRITERIA

A person is eligible for inclusion in the study if he/she:

- 1. Is between 18 and 40 years of age inclusively and has full legal capacity to volunteer;
- 2. Has read and signed an information consent letter;
- 3. Is willing and able to follow instructions and maintain the appointment schedule;
- 4. Is a neophyte who has no history of any previous contact lens handling experience;
- 5. Has a refraction cyl ≤1.00DC in either eye (after vertexing to corneal plane);
- 6. Has visual acuity ≤0.20 logMAR each eye with study lenses;
- 7. Demonstrates acceptable fit with study lenses;
- 8. Demonstrates the ability to successfully insert and remove the study lenses 3 times for each eye (contralateral CL handling, so that each lens type inserted and removed 3x on same eye);
- 9. Is willing to wear study CLs at least 5 days per week and 6 hours per day throughout the study

A person will be excluded from the study if he/she:

1. Is participating in any concurrent clinical or research study;

- 2. Has any known active* ocular disease and/or infection;
- 3. Has a systemic condition that in the opinion of the investigator may affect a study outcome variable;
- 4. Is using any systemic or topical medications that in the opinion of the investigator may affect a study outcome variable;
- 5. Has known sensitivity to the diagnostic pharmaceuticals to be used in the study;
- 6. Is pregnant, lactating or planning a pregnancy at the time of enrolment (by self-report);
- 7. Is aphakic;
- 8. Has undergone refractive error surgery;
- 9. Has taken part in another clinical research study within the last 14 days;
- 10. Any ocular and/or systemic conditions or concomitant medication to contraindicate contact lens wear or be expected to interfere with the primary outcome variables.
- * For the purposes of this study, active ocular disease is defined as infection or inflammation which requires therapeutic treatment. Mild (i.e. not considered clinically relevant) lid abnormalities (blepharitis, meibomian gland dysfunction, papillae), corneal and conjunctival staining and dry eye are not considered active ocular disease. Neovascularization and corneal scars are the result of previous hypoxia, infection or inflammation and are therefore not active.

5.2.4 REPEATED SCREENINGS

In some circumstances a repeated screening (Visit 1R) may need to be scheduled. Examples include, but are not limited to:

- 1. Incomplete information available at time of screening to determine eligibility (e.g. incomplete information about medical history.)
- 2. Study procedures unable to be completed in time scheduled for visit;
- 3. Study products not available at the time of the screening visit;
- 4. A transient health condition which may affect the eye(s) (e.g. a common cold, active allergies, fatigue etc;)
- 5. The short term use of medications (e.g. antibiotics, antihistamines etc.)
- 6. Reassessment of baseline ocular conditions (e.g. corneal and/or conjunctival staining, scars etc.)

The maximum total number of screenings permitted (per subject) will be 3.

5.3 STUDY MATERIALS

5.3.1 LENSES

Details on the lens type used in this study are listed in Table 1.

Table 1: Lens characteristics

Lens	Precision 1	1-Day Acuvue Moist
Material	Verofilcon A	Etafilcon A
Manufacturer	Alcon	Johnson & Johnson
HC licence #	101910	2519
Dk/t (barrer/cm)	100 (-3.00D)	25.5 (-3.00D)
Sphere power (D)	-0.50D to -6.00D	-0.50D to -6.00D
Base curve (mm)	8.3	8.5
Diameter	14.2	14.2
Replacement schedule	daily	daily

5.3.2 LENS CARE SYSTEM

A lens care system is not needed, because the lenses will be worn on a daily disposable basis and will be discarded at the end of each lens wear day.

5.3.3 REWETTING DROPS

Participants will not be provided with rewetting drops.

5.3.4 ORDERING CONSUMABLES

Precision1 lenses will be supplied by Alcon for the use in this study. A research assistant at CORE will order 1 day Acuvue Moist lenses from Johnson & Johnson, the cost for these lenses is included in the budget.

5.3.5 DISPOSING OF CONSUMABLES

Worn lenses collected during study visits and unworn lenses returned will be discarded as per University of Waterloo regulations. Contact lenses that were not dispensed to study participants may be returned to the sponsor, re-used for research purposes at CORE, or destroyed.

5.3.6 PRODUCT ACCOUNTABILITY

Accountability logs will be kept to include the number of lenses received, dispensed and unused. All products dispensed to participants will be recorded in the study binder using individual study participant accountability logs.

5.4 SCHEDULED AND UNSCHEDULED VISITS

This study has a total of 2 study visits, including the screening visit.

5.4.1 SCREENING

The investigator will determine participant eligibility using the inclusion and exclusion criteria. All participants who sign the consent letter will be assigned a study ID number. Ineligible participants will be discontinued from the study.

5.4.2 STUDY VISITS

Table 2 shows the summary of the 2 study visits. The total time commitment for each participant is 2hr 45 min. Participants who did not complete the handling training successfully at Visit 1, will return for Visit 1B-R (1hr) visit for additional handling training.

Visit code	Visits
1	Part A: Screening, Lens fitting (1hr) Part B: Handling training, Questionnaires, Lens dispensing (1hr)
1B-R	OPTIONAL: Handling Training (both CL types) & Dispense (only if px did not pass handling training at Visit 1) (1hr)
2	Follow-up and Exit (45 min)

Table 2: Summary of visits

Visit 1 -Part A - Screening and lens fitting (1hr)

The participant will attend the study visit wearing spectacles. The participant's eligibility for the study will be determined, including the following:

- Informed consent procedure
- Participant demographics (age, sex)
- Participant medical history/medications
- With habitual spectacles, logMAR high illumination high contrast visual acuity (HIHC VA) for OD, OS & OU
- Biomicroscopy examination (Efron scale)
 - External adnexa anomalies
 - Cornea & anterior eye assessment for scars, infiltrates
 - Bulbar & limbal redness
 - Corneal & conjunctival staining with fluorescein dye
 - Palpebral conjunctival hyperemia & roughness
- Auto refraction/auto keratometry: horizontal and vertical K readings;
- Subjective refraction/ best sphere refraction;
- Randomization: Lens type:
 - Precision 1 and 1-Day Acuvue Moist lenses will be randomized to one eye each;
- Study lens fitting –Lens types will be fit according to the randomization table the investigator will insert and remove the lenses
 - o logMAR high illumination high contrast visual acuity (HIHC VA) for OD, OS & OU;

- Power optimization if applicable;
- Lens fit assessment (Overall Lens Fit acceptance (0-4, 0.5 steps), Lens Wettability (0-4, 0.25 steps), Lens Tightness (0-100, 1 step), Lens Centration (0-3, 1 step)

С

• Confirmation of eligibility to continue to Visit 1 Part B.

Visit 1 – Part B – Handling training, questionnaires and lens dispensing (1hr)

- Randomization: Eye for contralateral handling:
 - Start eye for insertion/removal training will be randomized to prevent any potential bias due to handedness/dexterity
 - o Participant opens the lens blister packs and practices insertion & removal;
 - Insertion & removal with each lens needs to be successful 3x to be allowed to leave site with CLs
- Confirmation of eligibility capable of insertion/removal of CLs; participants who are NOT able to remove/insert the study lenses 3x will be offered to attend a re-training session (Visit 1B-R), at which the training will be repeated. Only those participants able to insert/remove lenses at Visit 1 (or Visit 1B-R) will continue in the study.
- **PRIMARY OUTCOME VARIABLE** (only if participants have passed the CL handling training): subjective post-handling training ratings (0-100 scale, where 100 means better handling) for **each eye individually**. Separate ratings and comments for:
 - Ease of insertion
 - Ease of removal
 - General handling questions (not primary outcome variable)
- LogMAR HIHC VA for OD, OS and OU (If returning for Re-training: habitual spectacles, if lenses are dispensed today: study CL)
- Lens wear instructions (only after a successful training)
- Booking of Follow-up visit(only after a successful training)
- Lens dispense (equal number of pairs as there are days until next visit day, plus 3 spare
 pairs in case of handling issues); each px will keep the same lens type (L1 or L2) for
 each eye as randomized to for handling training (e.g. if Precision1 was used on OD for
 training, Precision1 will be worn on OD for 1 week of wear) (only after a successful
 training)

Visit 1B-R: Handling Re-Training (optional) (1hr)

Those participants who did not pass the handling training at Visit 1 will repeat this
training, following the same randomization schedule as determined during Visit 1. If a
participant passes the handling training (i.e. they successfully inserted and removed
each lens 3x), the remaining steps from Visit 1, starting at "PRIMARY OUTCOME
VARIABLE", will be completed.

- **PRIMARY OUTCOME VARIABLE** (only if participants have passed the CL handling training): subjective post-handling training ratings (0-100 scale, where 100 means better handling) for **each eye individually**. Separate ratings and comments for:
 - Ease of insertion
 - Ease of removal
 - General handling questions (not primary outcome variable)
- LogMAR HIHC VA for OD, OS and OU (If returning for Re-training: habitual spectacles, if lenses are dispensed today: study CL)
- Lens wear instructions (only after a successful training)
- Booking of Follow-up visit(only after a successful training)
- Lens dispense (equal number of pairs as there are days until next visit day, plus 3 spare pairs in case of handling issues); each px will keep the same lens type (L1 or L2) for each eye as randomized to for handling training (e.g. if Precision1 was used on OD for training, Precision1 will be worn on OD for 1 week of wear) (only after a successful training)
- Participants who were unable to successfully complete the insertion/removal training will exit the study now.

Visit 2: 1-week follow-up and study exit, day 6-10 days after Visit 1 or Visit 1B-R

Participant to attend visit after 2 hours or more of contralateral study lens wear.

- Collect unused study CLs;
- Changes in medical history/medications;
- LogMAR HIHC VA for OD, OS and OU with study lenses
- Compliance (# of CL wear days; total and comfortable hours of wear);
- Subjective ratings for wear experience with both CLs (0-100 scale, where 100 means better performance; integer steps, ratings for each eye individually for a typical day in the last week);
 - Comfort (at insertion and just before removal)
 - Handling (insertion & removal)
 - General handling questions
- Preference ratings between study lenses:
 - Comfort
 - Handling for insertion
 - Handling for removal
 - Overall
 - Willingness to purchase
- Lens fit assessment (Overall Lens Fit acceptance (0-4, 0.5 steps), Lens Wettability (0-4, 0.25 steps), Lens Tightness (0-100, 1 step), Lens Centration (0-3, 1 step)
- Lens removal

Study Exit:

- Biomicroscopy examination (Efron scale) SAFETY
 - External adnexa anomalies
 - o Cornea & anterior eye assessment for scars, infiltrates

- Bulbar & limbal redness
- Corneal & conjunctival staining with fluorescein dye
- Palpebral conjunctival hyperemia & roughness
- Exit logMAR HIHC VA for OD, OS and OU (habitual spectacles) SAFETY;
- Study exit forms & remuneration.

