5.5 STUDY PROCEDURES

Table 3 summarizes the procedures at each visit. The order of procedures is described in sections 5.4.2.

Table 3: Summary of procedures to be conducted at scheduled visits

Procedure	Visit 1 Screening, fitting, handling training, CL dispense	Visit 1B-R Additional handling training	Visit 2 1-week follow up and Exit
Informed consent	x		Ĭ
Participant demographics (age, sex)	х		
Medical history and medications	х		
Changes in medical history/ medications		Х	X
HCVA (logMAR) (habitual spectacles)	х		Х
Biomicroscopy examination	х		Х
Auto refraction/auto keratometry: horizontal and vertical K readings	х		
Subjective refraction/ best sphere refraction	X		
Fitting of study lenses	х		20.00
Assessment of lens fit	х		X
Randomization	х		30 0
Lens insertion/ removal training	х	Х	
Subjective post-handling training ratings	х	Х	

HCVA (logMAR) (Contact lenses)	X	Х	Х
Lens wear instructions and lens dispense	X	Х	
Confirm eligibility	Х	Х	
Collection of unused study lenses			Х
Compliance questions			Х
Subjective ratings for wear experience and preference ratings			Х
Lens removal			х
Study exit documentation			Х

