5.5.3 VISUAL ACUITY

Visual acuity will be measured using high contrast computer-generated acuity charts.

Participants will be asked to read letters that progressively decrease in size on a computer screen located at a distance of 6 meters. Measurements will be taken during the subjective refraction, with study lenses and habitual spectacles.

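### At Visit 2 the eye-by-eye acuity test with the study lenses comes before the ratings and preference questions and could cue some participants to a vision difference between the lenses

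*Combined protocol and SAP*

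**What the plan says.** The Visit 2 list in section 5.4.2 starts with return of unused lenses and changes in medical history. It then continues, in this order:

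- acuity: "LogMAR HIHC VA for OD, OS and OU with study lenses";
- compliance: "Compliance (# of CL wear days; total and comfortable hours of wear";
- ratings: "Subjective ratings for wear experience with both CLs (0-100 scale, where 100 means better performance; integer steps", given as "ratings for each eye individually for a typical day" and covering comfort, handling and the general handling questions;
- preferences: "Preference ratings between study lenses", covering comfort, insertion, removal, overall and willingness to purchase;
- lens fit, then lens removal.

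Section 5.5 gives this list the force of a sequence: "The order of procedures is described in sections 5.4.2". Section 5.5.3 describes what the participant does in the acuity test: "Participants will be asked to read letters that progressively decrease in size on a computer screen". Section 5.1.3 describes the masking: "Participants and Investigators will be masked to which lens type (brand) the participants will be wearing in each eye".

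**The concern.** In a contralateral study the eye is the unit that carries the lens. A chart test of the right eye and then the left eye is therefore also a test of one lens and then the other. A participant can notice how far down the chart each eye gets without being told a score. Masking conceals the brand, not how each eye sees.

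The Visit 2 ratings are meant to sum up a typical day in the past week, and the preferences are meant to sum up the wear experience. A week of wear is mostly experience with both eyes open, whereas the chart test isolates each lens. The questionnaire has no separate vision item, so a fresh impression of vision can show only in the other answers. The two broadest questions, overall preference and willingness to purchase, are the likeliest place. The introduction names vision as the leading reason for dropout among new wearers (41%), so these participants may well give it weight. What is at stake is whether those answers reflect the week of wear alone or partly the clinic test that came just before.

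**Working it through.** No arithmetic bears on this point; it rests on the order of procedures. The one nearby figure, the 32 completers in section 5.2.1, is not in dispute. An exact two-sided paired t-test with effect size 0.60 and alpha 0.05 first reaches 90% power at n = 32 (power 0.908).

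**Step 1. Is the listed order the planned order?** Yes. Section 5.5 refers to section 5.4.2 for the order. Table 3 shows only which procedures belong to which visit.

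**Step 2. Where does eye-by-eye acuity with the study lenses fall relative to the questionnaires?**

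| Time | Acuity by eye with study lenses | Questionnaires |
|---|---|---|
| Visit 1 Part A (fitting) | Yes | None |
| Visit 1 Part B, or 1B-R if retrained (dispensing) | Yes, after the ratings | Primary ratings and general handling |
| Visit 2 | Yes, before the ratings and preferences | Ratings, then preferences |

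At Visit 2 only the compliance questions stand between the test and the ratings.

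**Step 3. Is there a safeguard?** No section says whether acuity results are shared with the participant or withheld, and none requires the questionnaires to be completed first.

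**Step 4. Could a difference between the eyes exist?** Section 5.2.3 allows cylinder up to 1.00 DC and acuity up to 0.20 logMAR in each eye with the study lenses. It sets no limit on the difference between eyes. Section 5.4.2 provides for power optimization at fitting, which would reduce such differences. A difference is possible, but the documents give no figure for one.

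**Step 5. Which way would a cue act?** Section 5.1.2 randomizes lens type to eye.
- A difference that belongs to the eye, such as residual cylinder or a naturally weaker eye, is not systematically tied to either lens. A cue from it adds noise.
- A difference that belongs to the lens would act in one direction across participants.

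**Step 6. Which outcomes are exposed?** Section 2 lists as Visit 2 endpoints the comfort and handling ratings, the preferences for insertion and removal handling, and the general handling ratings. None asks about vision, and a letter chart has little bearing on opening a package or judging whether a lens is inside out. Overall preference and willingness to purchase appear in sections 5.4.2 and 5.5.2 but not among the endpoints in section 2. The primary ratings are complete before Visit 2.

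**Step 7. Does anything at Visit 2 need acuity first?** Nothing stated. The Part A test supports an inclusion criterion, so it has to come early. The Visit 2 test with study lenses has no such role. The exit acuity that is marked as a safety measure is a separate test with spectacles, done after lens removal.

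**The case against.** The strongest reply is that the test tells participants little they do not already know. By Visit 2 they have worn the lenses for 6 to 10 days, on at least 5 days and for at least 6 hours a day, and for 2 hours or more that day. They have also had the same eye-by-eye test at fitting and at dispensing. If one lens does give better vision, that is a real property of the product and may properly inform an overall preference. This largely stands, and it keeps the point small. It does not give a reason to repeat the test immediately before the questions.

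Four stronger readings are tempting, and the documents do not support them:

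- *Participants learn which eye sees worse.* This needs a noticeable difference and a participant who notices it. The documents show no such difference and do not say that results are shared.
- *All Visit 2 subjective endpoints are compromised.* The listed endpoints contain no vision item, and the most exposed questions are not listed endpoints.
- *Visit 1 uses the opposite order, so the comparison of training with one week is confounded.* Part B does put ratings before acuity, but Part A has already tested each eye with the study lenses. A test of this kind precedes the ratings at both times.
- *The order favors one lens.* Randomizing lens to eye turns differences that belong to the eye into noise. A consistent direction would need a difference in vision between the lenses themselves, which the documents do not show.

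**Conclusion.** The point holds as a minor, avoidable weakness in the order of procedures. The planned Visit 2 sequence could cue some participants to a vision difference between lenses just before they compare them, and brand masking does not prevent this. Overall preference and willingness to purchase are most exposed, and the comfort and handling items less so. The Visit 2 order has no effect on the primary analysis.

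The size cannot be computed, because the documents give neither a between-eye acuity difference nor any relation between acuity and the answers. The conclusion assumes that staff follow the listed order, that some participants have a noticeable difference between the eyes, and that a chart test makes it more salient than a week of wear has done. If the last two fail, reordering gains nothing but also loses nothing.

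**What to change.** In the Visit 2 list of section 5.4.2, move the subjective ratings and the preference ratings ahead of the study-lens acuity test, and reorder the case report form pages to match. Lens fit already follows the questionnaires and can stay where it is. The acuity test is still done with the lenses in place, because lens removal remains the last step before the exit procedures. Every procedure and the 2-hour minimum wear stay unchanged.

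The cost is one edit to the list and the form pages, with no added procedure, participant or expected visit time. It has to be made before Visit 2 data are collected, because the order cannot be corrected in the analysis.

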5.4.3 UNSCHEDULED VISITS

An unscheduled visit is defined as an interim visit requested by the participant or investigator due to an unanticipated problem. Data recorded at these visits will be entered into the database. Only relevant and applicable unscheduled visit information will be included in the final report as deemed necessary by the lead investigator.

5.5 STUDY PROCEDURES

Table 3 summarizes the procedures at each visit. The order of procedures is described in sections 5.4.2.

Table 3: Summary of procedures to be conducted at scheduled visits

Procedure	Visit 1 Screening, fitting, handling training, CL dispense	Visit 1B-R Additional handling training	Visit 2 1-week follow up and Exit
Informed consent	x		Ĭ
Participant demographics (age, sex)	х		
Medical history and medications	х		
Changes in medical history/ medications		Х	X
HCVA (logMAR) (habitual spectacles)	х		Х
Biomicroscopy examination	х		Х
Auto refraction/auto keratometry: horizontal and vertical K readings	х		
Subjective refraction/ best sphere refraction	X		
Fitting of study lenses	х		20.00
Assessment of lens fit	х		X
Randomization	х		30 0
Lens insertion/ removal training	х	Х	
Subjective post-handling training ratings	х	Х	

HCVA (logMAR) (Contact lenses)	X	Х	Х
Lens wear instructions and lens dispense	X	Х	
Confirm eligibility	Х	Х	
Collection of unused study lenses			Х
Compliance questions			Х
Subjective ratings for wear experience and preference ratings			Х
Lens removal			х
Study exit documentation			Х

